### 3.2 Exclusion Criteria:

- 3.2.1 Pregnancy or breast-feeding (women of childbearing potential, any female who has experienced menarche and who has not undergone surgical sterilization or is post-menopausal with a positive serum pregnancy test).
- 3.2.2 Presence of steroid-refractory acute graft-versus-host disease (GVHD).
- 3.2.3 Patients that underwent allogeneic transplantation as a treatment of graft failure.
- 3.2.4 Dual refractory CMV reactivation to foscarnet and ganciclovir or evidence of CMV disease.

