## 4.0 Treatment Plan

### 4.1 Treatment Initiation:

Brentuximab will be given as an IV infusion over 30 minutes every 3 weeks for a total of 6 cycles. starting between days 35 and 60 post allogeneic SCT.

Brentuximab dose will be based on actual body weight starting with an initial dose of 1.2 mg/kg for the first 2 cycles and then the dose will be increased to 1.8 mg/kg after the second cycle for all subsequent cycles. Brentuximab dose will be based on actual body weight except for patients weighing more than 100 kg, then dose will be calculated based on 100 kg.

Patients must meet the following criteria to start any cycle of brentuximab:

1. Absolute neutrophil count > 1,000/mm^3 not requiring daily growth factor support on the day of the brentuximab infusion.
2. Platelet count greater than 50,000/mm^3 independent of platelet transfusions or thrombopoietin factor for at least 5 days.
3. No clinical evidence of life-threatening infection.

4. No active bleeding.
5. No uncontrolled acute GVHD (steroid refractory).
6. No CMV re-activation that is dual-refractory to foscarnet and ganciclovir/ No active CMV disease.
7. Creatinine < 1.5 mg/dL or creatinine clearance greater than or equal to 40 cc/min as defined by MDRD method from National Kidney Disease Education Program (NKDEP)
8. Serum bilirubin < 1.5 mg/dL
9. SGPT < 200 IU/L unless related to patient's malignancy

Vital sign monitoring, observation, and treatment of hypersensitivity reactions during and after infusion will be performed per standard of care.

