#### **4.4 Treatment will not be dose reduced or stopped for:**

1. New onset GVHD.
2. An infusion reaction, in which case the infusion will be interrupted and appropriate medical intervention will be administered. Pre-medicate subsequent infusions with acetaminophen, an antihistamine, and/or a corticosteroid.

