## 6.0 Study Criteria

### Off Study Criteria:

- 6.1 Patient withdraws consent.
- 6.2 Patient can not tolerate treatment.
- 6.3 Unexpected pattern of toxicity.
- 6.4 Presence of both steroid and 2nd line treatment refractory GvHD while on treatment with brentuximab.
- 6.5 Presence of dual-refractory CMV reactivation to foscarnet and ganciclovir or CMV end-organ disease while on treatment with brentuximab.

- 6.6 Patient's inability of unwillingness to have follow-up visits and/or laboratory tests required by this protocol.
- 6.7 One year after treatment completion.

**Steroid refractory GVHD** is defined as: absence of any response 7 days after the initiation of corticosteroids for skin GVHD or 10-14 days after its initiation for GI and liver GVHD. Patients who are steroid refractory are not eligible to be enrolled on protocol, however if a patient develops GVHD while on protocol, brentuximab will not be held.

**Secondary graft failure** is defined as a sustained declined of ANC  $<0.5 \times 10^9/L$  for 3 consecutive days after initial documented engraftment with no evidence of disease progression and is not associated with concomitant medication that is known to cause cytopenias.

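### For acute GVHD that turns steroid refractory on study, Section 4.1 bars the next cycle, but the Section 6.0 note, read literally, says brentuximab is not held

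*Combined protocol and SAP*

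**What the plan says.** Five provisions in the combined protocol and SAP deal with GVHD and treatment.

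- **3.2.2 (exclusion):** "Presence of steroid-refractory acute graft-versus-host disease (GVHD") is a bar to enrolment.
- **4.1 (cycle start):** the list opens with "Patients must meet the following criteria to start any cycle of brentuximab", and item 5 reads "No uncontrolled acute GVHD (steroid refractory").
- **4.4 item 1:** under the heading "Treatment will not be dose reduced or stopped for", the entry is "New onset GVHD".
- **6.4 (off study):** a patient leaves the study when GVHD is refractory to steroids and also to second-line treatment.
- **Section 6.0, definition of steroid-refractory GVHD:** no response at 7 days of corticosteroids for skin, or at 10-14 days for GI and liver. The note repeats that such patients cannot enrol. It then turns, with the word 'however', to patients already on study: "if a patient develops GVHD while on protocol, brentuximab will not be held".

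The discontinuation list in 4.3 does not mention GVHD. Nothing in the protocol ranks 4.1 above the Section 6.0 note or the reverse.

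**The concern.** The two instructions meet at a scheduled decision. Section 5.2 requires a GVHD assessment within 5 days before each cycle. If that assessment finds steroid-refractory acute GVHD, an investigator working from 4.1 withholds the cycle. One working from the Section 6.0 note, taken at its word, gives it.

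At stake is whether a patient with a serious transplant complication receives a dose that the cycle-start criteria forbid, and whether patients in the same state are treated alike. The study plans 20 patients (8.2), and the incidence of acute GVHD is one of its secondary objectives (1.2.4), so uneven handling of these cases would be awkward to describe afterwards.

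**Working it through.** No arithmetic settles the main point, because it depends on no rate, sample size or error level. The check is to take each GVHD state that can arise on study and read the rules against it.

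| State on study | 4.1 item 5 | 4.4 item 1 | Section 6.0 note, literal | 6.4 | Result |
|---|---|---|---|---|---|
| New onset, or responding to steroids | cycle allowed | no reduction or stop at new onset | not held | not met | consistent |
| Acute, steroid refractory, second line not failed | cycle barred | silent | not held | not met | conflict |
| Refractory to steroids and second line | cycle barred if acute | silent | not held | off study | 6.4 settles it |

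Only the middle row conflicts.

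**Does 4.1 item 5 apply after enrolment?** Yes. Its lead-in covers any cycle. Since 3.2.2 already keeps steroid-refractory acute GVHD out at entry, item 5 adds something only for GVHD that becomes refractory later. That can affect cycle 1 as well as cycles 2-6, if the change falls between enrolment and the first dose.

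**Does the note reach the refractory state?** Literally, yes. It sits inside the definition of steroid-refractory GVHD, contrasts on-study GVHD with the enrolment bar, and carves out no exception. It speaks of GVHD that develops on protocol, so the clash is plainest where the GVHD itself began on study and then failed steroids.

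**Can the state arise between two doses?** Yes. The cycle is 21 days (8.1) and the definition is met at 7 days (skin) or 10-14 days (GI, liver). The latest steroid start after one dose that still allows refractoriness to be declared by the next dosing day is:

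- skin: 21 - 7 = 14 days;
- GI or liver: 21 - 14 = 7 days to 21 - 10 = 11 days.

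If the 5.2 assessment is made 5 days before the dose, these become:

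- skin: 21 - 5 - 7 = 9 days;
- GI or liver: 21 - 5 - 14 = 2 days to 21 - 5 - 10 = 6 days.

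**Does another criterion remove the conflict?** Partly. Item 8 of 4.1 requires "Serum bilirubin < 1.5 mg/dL", so liver GVHD that raises bilirubin to that level or above bars the cycle anyway. The practical conflict is mainly in skin and GI disease.

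**The case against.** The best answer is that the provisions fit together on an ordinary reading. The note uses the term for steroid-refractory disease in its first half and drops it in its second, where it speaks only of developing GVHD. That describes onset, and it matches 4.4 item 1. Item 5 of 4.1 is specific, mandatory and placed in the treatment section; the note is a remark within a definition. Reading them together gives each rule a job: continue at onset, withhold when steroid refractory, off study after second-line failure. The literal reading would leave item 5 with almost nothing to do in later cycles.

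Most of this stands. The graded reading is the most coherent one, and it is the one the fix should adopt. But it has to be assembled from four places, and the sentence most directly about steroid-refractory GVHD appears to say otherwise. For CMV, the protocol uses essentially the same threshold at entry (3.2.4), cycle start (4.1 item 6), discontinuation (4.3 item 2) and off study (6.5). For GVHD, the entry and cycle-start threshold differs from the off-study threshold, and the note falls in the gap.

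Two stronger inferences are tempting, and the documents support neither.

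- A reader might take 6.4 to mean that dosing continues until second-line failure. But 6.4 is an off-study criterion; a patient can remain on study with a cycle withheld.
- A reader might conclude that the sponsor intends to dose through refractory GVHD, citing the hypothesis in 8.4 that CD30 down-regulation may lower GVHD incidence. That hypothesis concerns incidence and sets no dosing rule, and 4.1 item 5 points the other way.

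**Conclusion.** The conflict is real but narrow. It concerns acute GVHD that becomes steroid refractory after enrolment, for as long as second-line treatment has not failed. In that interval 4.1 item 5 bars the next cycle, the Section 6.0 note read literally does not, and no text says which prevails. Because following the note to the letter means giving a dose that 4.1 prohibits, it should be corrected rather than left as an optional clarification.

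The size cannot be put in numbers. The documents give no rate of steroid-refractory acute GVHD on brentuximab, so the number of affected patients cannot be derived. Cumulative dose is not a useful measure either, since it would only restate the dosing schedule; if a barred cycle is delayed rather than skipped, the difference is one of timing.

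A reader might also infer damage to the main result. The documents do not support that: the primary endpoint (secondary graft failure), the sample size and the stopping rule in 8.2 do not refer to this dosing rule and stand unchanged. Nor do the documents show that dosing in this interval causes harm. The consequence is limited to dosing safety and consistency between patients.

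The conclusion assumes that the note is meant as an operative instruction and that 4.1 means what it says about every cycle.

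**What to change.** Replace the last part of the Section 6.0 note with wording such as: *New-onset GVHD on study is not a reason to hold brentuximab. If acute GVHD is or becomes steroid refractory as defined here, no cycle is started until 4.1 item 5 is met again. Criterion 6.4 applies after second-line failure.* Add a cross-reference from 4.4 item 1 to 4.1 item 5. Tying the restart to item 5 uses a criterion that the protocol already has and avoids introducing a new, undefined standard of control.

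The cost is an amended note and one cross-reference. The downside is that a few patients may miss or delay cycles while their acute GVHD is steroid refractory, which 4.1 already requires.

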## 7.0 Expected Adverse Events and Reporting Requirements

Reporting requirements will adhere with the IRB policy 15.001. The adverse events (AEs) known to be related to brentuximab are listed in section 9.0 of this protocol.

Assessment of the Adverse Events Severity.

The severity of the AEs will be graded according to the Common Terminology Criteria v4.0 (CTCAE). Events not included in the CTCAE chart will be scored as follows:

General grading:

Grade 1: Mild: discomfort present with no disruption of daily activity, no treatment required beyond prophylaxis.

Grade 2: Moderate: discomfort present with some disruption of daily activity, require treatment.

Grade 3: Severe: discomfort that interrupts normal daily activity, not responding to first line treatment.

Grade 4: Life Threatening: discomfort that represents immediate risk of death.

Casualty Assessment.

For the purpose of this study adverse events known to be caused by brentuximab and its direct consequences will be scored as definitive related. When the relationship of the adverse event cannot be ruled out with certainty the AE may be considered probable or possible related. Adverse events known to be related to drugs used for supportive treatment will be scored as unrelated.

The principal investigator will be the final arbiter in determining the casualty assessment.

When possible, signs and symptoms indicating a common adverse event will be noted as 1 comprehensive event.

Events not to be considered AEs in this study are those related to original disease; changes in laboratory parameters such as electrolyte, magnesium and metabolic imbalances, uric acid changes, elevations of GPT, GOT, LDH and alkaline phosphatase. These would not be monitored.

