#### **8.3 Determination of hematologic toxicity and CMV disease**

The most common grade  $\geq 3$  side effects on brentuximab after allogeneic transplant(7) are neutropenia (24%), and thrombocytopenia (20%) which were reversible. CMV was detected in 5 patients and was clinically significant in 1 patient.

Brentuximab will be discontinued if patient develops dual foscarnet and ganciclovir-resistant CMV viremia or histologic CMV end-organ disease. In addition, the study drug will be reduced in all future patients if at any time there is >25% grade IV neutropenia rate or >10% CMV disease rate attributable to treatment observed within Day 45- Day 180.

These rates will be monitored in a continuous fashion.

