### 9.7 Adverse Events

9.7.1 The most common adverse reactions (seen in  $\geq 20\%$  of patients) include neutropenia, anemia, thrombocytopenia, peripheral sensory neuropathy, fatigue, nausea, vomiting, diarrhea, pyrexia, rash, cough and upper respiratory tract infection

9.7.2 Serious but less common adverse reactions include serious infections and opportunistic infections, tumor lysis syndrome, progressive multifocal leukoencephalopathy (PML), Stevens-Johnson syndrome, and embryo-fetal toxicity.

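### Section 7.0 gives two mandatory relatedness scores that can fit the same neutropenia and no order of precedence, and Section 8.3 does not say what counts as attributable

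*Combined protocol and SAP*

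**What the plan says.** Section 7.0 sets out how relatedness is scored, in four steps.

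- Known brentuximab reactions: "adverse events known to be caused by brentuximab and its direct consequences will be scored as definitive related". The list is given by reference: "The adverse events (AEs) known to be related to brentuximab are listed in section 9.0 of this protocol". In that list, Section 9.7.1 says that the most common reactions "include neutropenia, anemia, thrombocytopenia, peripheral sensory neuropathy, fatigue" and others.
- Uncertain cases: "When the relationship of the adverse event cannot be ruled out with certainty the AE may be considered probable or possible related".
- Supportive drugs: "Adverse events known to be related to drugs used for supportive treatment will be scored as unrelated".
- Final decision: "The principal investigator will be the final arbiter in determining the casualty assessment".

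Section 6.0, in defining secondary graft failure, sets aside falls in neutrophil count that are associated with other medicines known to lower blood counts. The protocol therefore expects such medicines in some of these patients.

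Section 8.3 reduces the study drug for everyone treated later whenever "there is >25% grade IV neutropenia rate or >10% CMV disease rate attributable to treatment observed within Day 45- Day 180". Both rates are to be monitored continuously.

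**The concern.** The first and third scoring instructions are both mandatory and both work by category of event. A grade IV neutropenia in a patient who is also on a supportive drug known to lower neutrophils can fit each of them. The middle category would be the natural place for such an event, but its wording is permissive. The arbiter is named but is given no criterion. The score of an overlapping event is therefore left to discretion, and one of the two mandatory instructions moves it out of the related count.

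This matters because the trial has no control group against which an attributed rate could be checked. It also matters because at least one limit in Section 8.3 depends on attribution. If events that brentuximab may have caused are scored as unrelated, an attributed rate can stay at or below its limit when the all-cause rate is above it.

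**Working it through.** **Inputs from the documents.** Sample size 20 (Section 8.2). Limits above 25% for grade IV neutropenia and above 10% for CMV disease, monitored continuously (Section 8.3). The attribution rule has no figure of its own. The one computed figure in Section 8 is the interval for a 5% graft-failure incidence in 20 patients. It reproduces as a Wald interval: 0.05 ± 1.96 × √(0.05 × 0.95 / 20) = 0.05 ± 0.0955, that is 0 to 14.55% with the lower end cut at zero, against the stated 0–14.6%. It serves here only to confirm n = 20.

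**Step 1: which rates depend on attribution.** In Section 8.3 the attribution phrase stands directly after the CMV disease rate.

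- Reading A: it qualifies both rates. Section 7.0 scoring then changes the neutropenia count.
- Reading B: it qualifies CMV disease only. Grade IV neutropenia is then counted whatever its cause, and Section 7.0 scoring cannot change it.

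The text does not settle this. Under either reading it does not say whether definitive only, or also probable and possible, counts as attributable.

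**Step 2: how many rescored events matter at n = 20.**

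- Neutropenia (Reading A): 6/20 = 30% exceeds 25%; 5/20 = 25.0% does not. One rescored event is enough. All-cause counts of 7, 8 and 10 need 2, 3 and 5 events rescored.
- CMV disease: 3/20 = 15% exceeds 10%; 2/20 = 10.0% does not. One event again decides, but the neutropenia overlap does not itself change this count.

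The same holds at earlier looks. For neutropenia, 3/10 = 30% exceeds the limit and 2/10 = 20% does not; 5/16 = 31.25% exceeds it and 4/16 = 25.0% does not.

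**Step 3: illustration under Reading A.** The documents give neither a true grade IV rate nor the share of events that would be scored unrelated, so both are assumptions. The 24% in Section 8.3 is for grade 3 or higher, not grade IV. Attributed rate = true rate × (1 − share excluded). The single-look column is the binomial probability of at least 6 events in 20. The any-look column is an exact recursion with a look after every patient from the 10th. It treats each patient's outcome as known at once.

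| True all-cause rate | Share scored unrelated | Attributed rate | Single look, n = 20 | Any look from patient 10 |
|---|---|---|---|---|
| 24% | 0 | 24% | 0.34 | 0.63 |
| 24% | 25% | 18% | 0.14 | 0.40 |
| 24% | 50% | 12% | 0.03 | 0.17 |
| 30% | 0 | 30% | 0.58 | 0.81 |
| 30% | 25% | 22.5% | 0.28 | 0.58 |
| 30% | 50% | 15% | 0.07 | 0.28 |
| 40% | 0 | 40% | 0.87 | 0.96 |
| 40% | 25% | 30% | 0.58 | 0.81 |
| 40% | 50% | 20% | 0.20 | 0.48 |

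With looks from the very first patient, the 30% rows become 0.89, 0.74 and 0.51.

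The any-look column is closer to the plan. The rule acts on future patients, and none remain at n = 20. A first crossing cannot even occur there: 6/20 requires at least 5/19 = 26.3% one patient earlier, which already exceeds 25%.

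**The case against.** Four objections carry weight.

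1. **The link to the neutropenia limit depends on the reading.** Under Reading B, grade IV neutropenia is already counted regardless of cause and the limit is untouched. This stands. The effect on the neutropenia limit can only be stated conditionally.

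2. **Section 7.0 can be read as an ordinary graded scheme.** It speaks of events known to be related to supportive drugs, not of every event in a patient who takes one. An event with two possible causes could go to the middle category, and the principal investigator gives it a single score. This stands in part: no event keeps two scores. But the middle category is optional, while the instructions either side of it are mandatory, and the arbiter has no written criterion.

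3. **The overlap is not quantified.** The documents name no particular supportive drug as a cause of neutropenia, and Section 6.0 speaks only in general terms. This stands, and it is why the table is illustrative.

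4. **Other safeguards do not use the Section 7.0 score.** The hematologic criteria in Sections 4.2 and 4.3 and the cohort-level toxicity rule in Section 8.1 carry no attribution wording. The graft-failure stopping rule in Section 8.2 uses the definition in Section 6.0. The hematologic toxicity objective in Section 1.2 is not restricted to related events, so a downward bias in that objective is not shown. This stands and limits the reach of the point to Section 8.3 and to any rate reported by attribution.

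A reader might infer from the table that the safety rule loses nearly all its sensitivity, from 58% to 7%. The documents do not support that. The arithmetic is right, but it needs Reading A, an assumed 30% rate, an assumed exclusion of half the events, and a single look at n = 20. Under the same two assumed rates with looks from patient 10, the fall is from 0.81 to 0.28.

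**Conclusion.** The point holds in a limited form. Section 7.0 has two mandatory scoring instructions that can both fit neutropenia, with no precedence between them. Section 8.3 leaves open whether attribution covers neutropenia and which categories count. This is a stated rule that can take possibly drug-caused events out of a safety count, so it deserves correction.

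Its certain size is small in number but can be decisive. If attribution covers neutropenia, one event rescored at the threshold (6/20 to 5/20) keeps the rate from exceeding 25%. If it does not, the Section 8.3 neutropenia rate is unaffected. Beyond that, the size depends on a true rate and an overlap share that the documents do not give.

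Two stronger readings should be set aside. One is that the CMV limit is weakened in the same way. That limit does depend on attribution, so the categories need defining, but nothing in the documents shows how CMV disease would come to be scored unrelated through a supportive drug. The other is that Section 8.3 must be changed to count all causes from the first dose. That would rewrite the trigger and the window of a dose-reduction rule, and the conflict in Section 7.0 gives no ground for it.

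**What to change.** **Section 7.0.** Replace the automatic supportive-drug sentence. An event with both a plausible brentuximab cause and a plausible supportive-drug cause should be scored at least possibly related. The unrelated category should be kept for events in which brentuximab has been ruled out.

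**Section 8.3.** Reconcile the wording with Section 7.0. State that definitive, probable and possible all count as attributable, and state whether the neutropenia limit is all-cause or attributed.

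**Reporting.** Give all-cause rates of grade IV neutropenia and CMV disease beside the attributed rates, so that the effect of attribution can be seen.

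Leave the two limits, the Day 45–180 window and the dose action unchanged.

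The cost is a change of wording in two sections and no new data. Attributed counts will be slightly higher, by the number of overlapping events. If attribution is confirmed to cover neutropenia, the limit may be reached somewhat sooner.

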#### **4.2 Dose Modification:**

Dose will be reduced from 1.8 mg/kg to 1.2 mg/kg or from 1.2 mg/kg to 1 mg/kg or from 1 mg/kg to stop treatment if:

1. Neutropenia grade 3-4 unresponsive to G-CSF or grade 4 thrombocytopenia are observed.
2. Peripheral neuropathy, new or worsening grade 2 or 3. Withhold treatment until improvement or return to grade 1 or baseline; then resume with a dose reduction.

Dose will be reduced to 1 mg/kg if:

1. Creatinine clearance < 30 cc/min as defined by MDRD method from NKDEP.  
<http://nkdep.nih.gov/lab-evaluation/qfr/estimating.shtml>
2. Hepatic impairment defined as bilirubin > 2 mg/dL.

If the patient develops grade 3-4 neutropenia unresponsive to G-CSF: Hold until resolution to grade </= 1 and restart at lower dose.

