**5.2 At each subsequent cycle (within 5 days prior to receiving first dose of brentuximab in each cycle):**

1. Physical exam including toxicity and GVHD assessment.
2. CBC with diff and platelets, chemistries.
3. Correlative studies: blood sample prior to the brentuximab dose.

**5.3** If patient has a biopsy (skin, GI or liver) at any time for GVHD diagnosis, a blood sample (10 mL) will be taken at that time for correlative studies.

**5.4** To be performed at approximately 1, 3, 6 and 12 months post-transplant.  
These evaluations follow our standard practice and are done to monitor engraftment and disease status. If clinically indicated these studies may be done at other time points which can replace the nearest planned timepoint.

1. Chimerism studies from peripheral blood performed on separated T-cells and myeloid cells.
2. At each visit, physical examination and adverse event documentation including GvHD assessment.
3. Disease specific assessment with bone marrow aspirate with cytogenetics, serum immunoglobulins in peripheral blood and CT for lymphoma staging as indicated.

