## 8.0 Statistical Considerations

Study Design

- 8.1 This is a phase II study in which brentuximab will be initiated after transplant (approximately day 35-60) post engraftment and restaging at day 30 (+10 days) and continued every 21 days for 6 cycles. Dose initiation will be at 1.2 mg/kg for 2 cycles and escalated to 1.8 mg/kg on subsequent 4 cycles. If greater than grade 3 toxicity seen at 1.2 mg/kg dose level then dose will be decreased to 1 mg/kg for all patients at initiation with subsequent cycles at 1.2 mg/kg dose. We will allow intrapatient dose modification based on toxicity.

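### Section 7 excludes GPT/GOT elevations of every grade from adverse events and from monitoring, although SGPT is a condition for starting every cycle

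*Combined protocol and SAP*

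**What the plan says.** Section 7.0 adopts CTCAE v4.0 grading and a causality assessment for adverse events. It then lists what is not an adverse event, beginning "Events not to be considered AEs in this study are those related to original disease; changes in laboratory parameters such as electrolyte, magnesium and metabolic". The list runs on through further chemistry results and ends with "elevations of GPT, GOT, LDH and alkaline phosphatase. These would not be monitored". There is no exception for grade, attribution or effect on dosing.

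Section 4.1 introduces its dosing conditions with "Patients must meet the following criteria to start any cycle of brentuximab". Item 9 is "SGPT < 200 IU/L unless related to patient's malignancy", and item 8 is a separate hepatic condition, "Serum bilirubin < 1.5 mg/dL". Section 3.1.6 uses the same SGPT limit for entry.

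Section 5.2 requires "CBC with diff and platelets, chemistries" within 5 days before each subsequent cycle, and Section 5.1 requires the same before the first. The analytes in the chemistry panel are not listed.

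Section 4.2 has one hepatic dose-modification trigger, based on bilirubin: "Hepatic impairment defined as bilirubin > 2 mg/dL".

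Section 8.1 contains a rule that acts on all patients: "If greater than grade 3 toxicity seen at 1.2 mg/kg dose level then dose will be decreased". It is not restricted to hematologic toxicity.

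**The concern.** One section says an enzyme will not be monitored, while another makes its value a condition for every dose. Both cannot be followed literally. If staff follow Section 7.0 for adverse-event recording, a patient can fail the Section 4.1 condition because of SGPT, or have a severe rise in GPT or GOT, and no graded and attributed adverse event results.

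What is at stake is the completeness of general safety reporting. Section 2.6 gives the safety of brentuximab early after transplant as a purpose of the study. Dosing starts at days 35 to 60. In the post-allogeneic experience summarized in Section 2.5, the median interval from transplant to first dose was 42 months (range 6 to 116), so that experience says little about tolerability this early. Section 9.7 lists no liver enzyme event among the drug's known reactions, so the exclusion cannot be explained as dropping a known drug effect.

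There is also a possible operational consequence. If the Section 8.1 rule is applied from adverse-event records, an excluded grade 4 enzyme elevation would not reach it.

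**Working it through.** The plan gives no figure for this point. The one computed design figure, the graft-failure interval of 0-14.6% in Section 8.2, reproduces as 0.05 + 1.96 × √(0.05 × 0.95 / 20) = 14.55%, with the lower limit of -4.55% truncated at 0. The point does not depend on it. The check is a comparison of sections.

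1. **Same analyte.** Section 7.0 says GPT and Section 4.1 says SGPT. These are two names for one enzyme, so the exclusion and the dosing condition concern the same laboratory value.
2. **Is it measured?** The Section 4.1 condition applies to any cycle and cannot be applied without a result. Sections 5.1 and 5.2 supply a chemistry panel before each dose. Read literally, the non-monitoring statement is incompatible with both.
3. **Is it recorded as an adverse event?** Section 7.0 says no, at every grade. A rise that fails the Section 4.1 condition is treated like a trivial one.
4. **Does another rule capture it?** Section 4.2 defines hepatic impairment by bilirubin only, so an isolated transaminase rise triggers no dose modification there. The off-study criterion for an unexpected toxicity pattern (Section 6.3) sets no recording requirement for it.
5. **Does it count under Section 8.1?** That rule refers to toxicity, not to adverse events. The documents do not say whether a laboratory change excluded under Section 7.0 is toxicity for this purpose.
6. **Is the dosing condition the same as severe?** This cannot be determined. The documents give neither an upper limit of normal nor the CTCAE enzyme cut-points, so 200 IU/L cannot be mapped to a grade. Grade and effect on dosing therefore have to be separate recording criteria.

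**Why no size is claimed.** With 6 cycles and 20 patients there are at most 6 × 20 = 120 pre-cycle panels. The 20 first panels precede study drug, leaving at most 5 × 20 = 100 after exposure. These count blood draws, not missed events. The documents give no rate of SGPT at or above 200 IU/L. Purely as an assumption, take a per-patient rate q. The chance of at least one such patient among 20 is 1 − (1 − q)^20, which is 33% for q = 2%, 64% for 5%, 88% for 10% and 96% for 15%. This shows only that the situation could plausibly arise in a trial of this size.

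**The case against.** The strongest reply is that the protocol defines safety narrowly. Section 8.2 defines it as no more than two secondary graft failures within 6 months of transplant. Section 1.1 names graft failure as the only primary objective, and no Section 1.2 objective concerns the liver. This stands: the primary conclusion and the stopping rule do not change.

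Three stronger readings are tempting, and the documents do not support them.

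- **That hepatic toxicity would go unrecorded altogether.** The exclusion names enzymes and does not name bilirubin, although its open-ended list leaves bilirubin's status uncertain. Bilirubin has its own condition in Section 4.1 and its own trigger in Section 4.2. GVHD is assessed at each cycle, and Section 6.0 covers liver GVHD. Clinical hepatic events are not expressly excluded.
- **That missed cycles could not be explained.** The laboratory results must exist for Section 4.1 to be applied, and nothing says that reasons for withheld doses go uncaptured. A rate of SGPT at or above 200 IU/L could still be computed from source records. What is lost is the graded and attributed adverse-event entry.
- **That 120 results are lost to the safety analysis.** Most panels may be normal, and a normal panel is never an adverse event.

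It can also be said that the non-monitoring statement means only that these values are not followed as adverse events, and that reporting follows an institutional policy not included in the documents. The first reading would remove the conflict over measurement but would leave severe and dose-blocking elevations unrecorded. The second cannot be checked. Keeping low-grade laboratory noise out of the record is reasonable, but the exclusion as written goes well beyond that.

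**Conclusion.** The concern holds in a limited form. Section 7.0 contradicts Sections 4.1, 5.1 and 5.2 on whether GPT is monitored. As written, it keeps GPT/GOT elevations that are severe, or that delay or omit a cycle, out of the adverse-event record. Whether they count toward the Section 8.1 toxicity rule is left open.

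The effect is on general safety reporting and possibly on that rule. It does not reach the graft-failure endpoint or its stopping rule, and the underlying values are retained in source records. No magnitude is claimed because the documents give no event rate.

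The conclusion assumes that Section 7.0 is followed literally and that the unseen institutional policy does not override it. It should be corrected, but it does not undermine the primary analysis. No view is taken on the SGPT threshold or on any dosing rule.

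**What to change.** Change recording only:

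- In Section 7.0, limit the enzyme exclusion to grade 1-2 elevations that do not affect dosing.
- Require GPT/GOT elevations to be recorded as adverse events and graded by CTCAE v4.0 if they are grade 3 or higher, or if they delay or omit a cycle under Section 4.1 item 9.
- Remove the non-monitoring statement for GPT and GOT, so that Section 7.0 agrees with Sections 4.1, 5.1 and 5.2.
- State in Section 8.1 or Section 7.0 whether these events count toward the rule for toxicity above grade 3.

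The cost is a short wording amendment and some additional adverse-event entries, probably few among 20 patients, though the documents give no rate to confirm this. The chemistries are already drawn and the grading system is already specified, so no new test, visit or dosing rule is needed.
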